## 6.5.1. Concomitant Medications for Treatment of Psoriasis

## 6.5.1.1. Topical Therapy

Use of topical psoriasis treatment (eg, corticosteroids, tar, anthralin, calcipotriene, tazarotene, methoxsalen, pimecrolimus, tacrolimus) is permitted at the investigator's discretion from Screening Visit S1 up to Week 4. The treatment should only cover a maximum of 20% body surface area, ie, for the scalp, the intertriginous regions, palms/soles. However, Class IV topical corticosteroids (alone or in combination) and phototherapy are prohibited until end of the study. Shampoos (containing tar or salicylic acid only) and topical moisturizers are allowed throughout the study, but participants should not use these topical agents (shampoos, moisturizers) on the day of a study visit. Nonmedicated shampoos may be used on the day of the study visit. Traditional Taiwanese, Korean, or Chinese medicines are prohibited during the study.

## 6.5.1.2. Phototherapy or Systemic Therapy for Psoriasis

The use of phototherapy or systemic antipsoriatic medications is not permitted at any time during the study. These medications include those targeted for reducing TNF (including but not limited to infliximab or etanercept), drugs targeted for reducing IL-12/23, IL-17, or IL-23 (including but not limited to ustekinumab, tildrakizumab [MK3222], risankizumab, secukinumab [AIN457], ixekizumab [LY2439821], or brodalumab [AMG827]), alpha-4 integrin antagonists (including but not limited to natalizumab), steroids, any conventional systemic therapy that could affect psoriasis or the IGA evaluation (including but not limited to MTX, cyclosporine, acitretin), herbal treatments, or traditional Taiwanese, Korean, or Chinese medicines, and any other biological agent or other systemic medication that could affect psoriasis or the IGA evaluation.

#### 6.5.2. Concomitant Medications for Conditions Other than Psoriasis

Every effort should be made to keep participants on stable concomitant medications. If the medication is temporarily discontinued because of abnormal laboratory values, side-effects, concurrent illness, or the performance of a procedure, the change and reason for it should be clearly documented in the participant's medical record. The use of stable doses of nonsteroidal anti-inflammatory drugs is allowed. However, disease-modifying agents such as MTX, sulfasalazine, or IM gold are prohibited during the study. Antimalarial agents, except for chloroquine, may be used after Week 40. The use of corticosteroids for indications other than psoriasis should be limited to situations for which, in the opinion of the treating physician, there are no adequate alternatives. They should be used on a short-term basis, preferably for  $\leq 2$  weeks. Longer-term use of corticosteroids should be discussed with the Medical Monitor or designee and may require discontinuation of study drug. Inhaled, otic, ocular, nasal, or other routes of mucosal delivery of corticosteroids are allowed throughout the study.

#### 6.5.3. Concomitant Medications of Special Interest

Every effort should be made to keep participants on stable concomitant medications. If the medication is temporarily discontinued because of abnormal laboratory values, side-effects, concurrent illness, or the performance of a procedure, the change and reason for it should be clearly

documented in the participant's medical record. The Sponsor must be notified in advance (or as soon as possible thereafter) of any instances in which prohibited therapies are administered.

Details on permitted and prohibited concomitant medication relevant to the study is presented in Table 1. The medications detailed in the table are prohibited as they are known to affect CFR measurements or interact adversely with adenosine.

Table 1: Concomitant Medication of Special Interest

Drug class	Effect on CFR	Strength of evidence	Study rules
Products containing short- acting xanthine derivates eg, caffeine, etc. This includes beverages such as coffee, black/green tea, cola drinks	Decreases	Good	Allowed in the study but prohibited 12 hours before CFR procedure.
Drugs containing long- acting xanthine derivates eg, theophylline, diprophylline	Decreases	Good	Prohibited in study
Phenylephrine containing products	Increases	Good	Prohibited in study
NSAIDs*	Increases	Good	Allowed in stable dosing for at least 3 months before study. Prohibited are intermediate use >14 days and use on the day before and day of CFR measurement
ACEi	Increases	Good	Allowed in stable dosing for at least 3 months before study
ARBs	Losartan, no effect  Candesartan, increases	Moderate	Allowed in stable dosing for at least 3 months before study
Thiazide diuretics	No data available		Allowed in stable dosing for at least 3 months before study
Loop diuretics	No data available		Allowed in stable dosing for at least 3 months before study
Vitamin K antagonists	No data available		Prohibited in study
Platelet inhibitors (including ≤100mg ASA/d)	Increases	Good	Prohibited in study
Beta-blockers	First and second generation: Contradictory data Third generation: Increased	Good Moderate	Prohibited in study
Aldosterone blockers	Increases	Moderate	Prohibited in study
Calcium antagonists Sodium channel inhibitors (ranolazine)	Increases Increases	Good Moderate	Prohibited in study Prohibited in study
Statins	Increases (if therapy >8 weeks)	Good	Prohibited in study
Glucose lowering drugs	Insulin: Increases DPP4i: Mixed effects	Moderate Moderate	Prohibited in study
	GLP 1 RA: No effect	Moderate	
	SU: Decreases/no effect	Moderate/good	
	Metformin: Increases	Moderate/good	

CONFIDENTIAL - FOIA Exemptions Apply in U.S.

Drug class	Effect on CFR	Strength of evidence	Study rules
Products containing short- acting xanthine derivates eg, caffeine, etc. This includes beverages such as coffee, black/green tea, cola drinks	Decreases	Good	Allowed in the study but prohibited 12 hours before CFR procedure.
	TZD: No effect	Moderate	
	SGLT2 inhibitors: Increases	Good	
Hawthorn derivates	Increases	Good	Prohibited in the study

Table 1: Concomitant Medication of Special Interest

ACEi= angiotensin-converting enzyme inhibitors; ARB= angiotensin II receptor blockers; CFR= coronary flow reserve; DDP4i= Dipeptidyl peptidase 4 inhibitors; GLP-1 RA= Glucagon-like peptide-1 receptor agonists; NSAID= nonsteroidal anti-inflammatory drugs; SU= sulfonylurea; TZD= thiazolidinediones; SGLT2= sodium glucose co-transporter 2

#### 6.6. Dose Modification

Dose or dosage adjustment of guselkumab is not permitted during the study.

## 6.7. Intervention After the End of the Study

No continued access to guselkumab is proposed for this study. At the end of their participation in the study, the participants will be instructed that they should return to their primary physician to determine standard of care, if applicable.

# 7. DISCONTINUATION OF STUDY INTERVENTION AND PARTICIPANT DISCONTINUATION/WITHDRAWAL

## 7.1. Discontinuation of Guselkumab

A participant's guselkumab regimen must be discontinued if:

- The participant withdraws consent to receive guselkumab.
- The investigator believes that for safety reasons or tolerability reasons (eg, AEs) it is in the best interest of the participant to discontinue guselkumab.
- The participant becomes pregnant. Refer to Appendix 14, Contraceptive Guidance and Collection of Pregnancy Information.
- The participant is diagnosed with a malignancy (except 1-2 localized basal cell skin cancers that are treated with no evidence of recurrence or residual disease).
- The participant meets any of the following TB screening criteria:

A diagnosis of active TB.

Has symptoms suggestive of active TB based on follow-up assessment questions and/or physical examination or has had recent close contact with a person with active TB and cannot or will not continue to undergo additional evaluation.

Has a chest radiograph with evidence of current active TB and/or a positive QuantiFERON-TB Gold test result unless active TB can be ruled out and appropriate treatment for latent TB can be initiated before the next administration of guselkumab and

continued to completion. Participants who have an indeterminate result should have the test repeated. Guselkumab must be discontinued for participants with persistently indeterminate QuantiFERON-TB Gold test results .

Discontinues treatment for latent TB prematurely or is noncompliant with the therapy.

- The participant is unable to adhere to the study visit schedule or comply with protocol requirements.
- The participant develops an allergic reaction such as bronchospasm with wheezing and/or dyspnea requiring ventilatory support, or symptomatic hypotension that occurs following a guselkumab administration.
- The participant has a reaction resulting in myalgia and/or arthralgia with fever and/or rash (suggestive of serum sickness and not representative of signs and symptoms of other recognized clinical syndromes) occurring 1 to 14 days after an injection of guselkumab. These may be accompanied by other events including pruritus, facial, hand, or lip edema, dysphagia, urticaria, sore throat, and/or headache.
- Participants who develop a serious or opportunistic infection. Discussion of such participants with the Medical Monitor or designee should also be considered.
- The participant receives a concomitant medication that is prohibited by the protocol.
- The study is terminated by the Sponsor.

If a participant permanently discontinues guselkumab before Week 28, the Final Efficacy Visit should occur at the time of discontinuation or as soon as possible, and all assessments scheduled for the Final Efficacy Visit should be performed. The participant should also return for a Final Safety Visit, 12 weeks after the last guselkumab dose.

If the reason for withdrawal from the study is withdrawal of consent, then no additional assessments are allowed. If a participant discontinues study treatment and starts another biologic treatment, an interval of at least 12 weeks between the last guselkumab administration and the start of the new treatment is recommended. The number of dropouts in the study are expected to be low; however, additional participants will be entered to maintain the sample size and ensure that the protocol-specified number of participants complete the study.

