## 2.3.1. Risks for Study Participation

Potential Risks of	Summary of Data/							
Clinical Significance	Rationale for Risk	Mitigation Strategy						
Potential Risks Due to Guselkumab								
Serious infections and reactivation of latent infections	Available animal and human data suggest that blockade of IL-23 may be associated with an increased infection risk.	
 
Participants with a history of, or ongoing, chronic or recurrent infectious disease, including human immunodeficiency virus (HIV), Hepatitis B or C virus (HBV, HCV), will be excluded from the study. Similarly, participants with evidence of active or untreated latent tuberculosis (TB) will be excluded from the study (Section 5.2).
 
Participants who have received a live viral or bacterial vaccination within 12 weeks of Week 0 will be excluded from the study. In addition, participants must agree not to receive a live viral or live bacterial vaccination during the study and for 12 weeks after receiving the last dose of guselkumab (Section 5.2).
 
Participants will be instructed to seek medical attention if they develop signs or symptoms suggestive of an infection, and investigators are instructed in the protocol to monitor for signs or symptoms of infections, including TB (Section 8.2.5).
 
Discontinuation of a participant's guselkumab must be strongly considered if the participant develops a serious infection, including but not
 
						

CONFIDENTIAL – FOIA Exemptions Apply in U.S.

Hymoropolitivity recetions	Carious hymanassaitivity	limited to sepsis or pneumonia. In addition, any serious infection should be discussed with the medical monitor or designee, and guselkumab should be withheld until the clinical assessment is complete (Sections 5.2, 7.1).

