Hypersensitivity reactions, including serious hypersensitivity reactions.	Serious hypersensitivity reactions including anaphylaxis have been reported in post-marketing experience with guselkumab in psoriasis patients.	
 
Participants with known allergy, hypersensitivity, or intolerance to guselkumab or its excipients will be excluded from the study.
 
Sites are instructed that before any administration of guselkumab, appropriately trained personnel and medications (eg, injectable epinephrine) must be available to treat hypersensitivity reactions, including anaphylaxis. In addition, all participants must be observed carefully for signs and symptoms of a hypersensitivity reaction (eg, urticaria, pruritis, angioedema, wheezing, dyspnea, or hypotension).
 
Any participant who develops a serious hypersensitivity reaction such as anaphylaxis must discontinue guselkumab (Section 7.1).
 

Malignancy	The preponderance of preclinical data suggests that blockade of endogenous IL-23 would not be detrimental and may in fact be beneficial in tumor immunosurveillance and host protection; however, a risk of malignancy cannot be excluded.	
 
Those participants who currently have a malignancy or have a history of malignancy within 5 years prior to screening (with exceptions noted in Section 5.2) will be excluded from the study.
 
During the conduct of the study, participants will undergo regular clinical monitoring including routine safety labs to assess for any changes in health status that may indicate a possible malignancy.
 
Participants who develop a malignancy during the study (with the exception of no more than 2 localized basal cell skin cancers that are treated with no evidence of recurrence or residual disease) will be discontinued from guselkumab (Section 7.1).
 

Liver injury	A SAE of 'toxic hepatitis' was reported in the ongoing Phase 2/3 guselkumab Crohn's disease program in a participant who received guselkumab 1200 mg IV at Weeks 0, 4, and 8, and 200 mg SC at Week 12. Based on the hepatocellular pattern of injury, temporal relationship of the event to guselkumab exposure, and the exclusion of alternative etiologies, this event may represent drug-induced liver injury possibly related to guselkumab.	Participants with marked liver enzyme elevations or symptoms or signs of liver dysfunction (eg, jaundice), should undergo a thorough investigation for possible causes of liver injury (Section 5.1).

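### Section 7.1 requires guselkumab to be stopped for a serious infection, but Section 2.3.1 and Appendix 15 item 6 leave that stop to judgement

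*Protocol*

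**What the plan says.** Protocol Section 7.1 introduces its list with "A participant's guselkumab regimen must be discontinued if". One entry is "Participants who develop a serious or opportunistic infection". The only optional element in that entry is an added discussion with the Medical Monitor.

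The risk table in Protocol Section 2.3.1 covers the same event in its row on serious infections: "Discontinuation of a participant's guselkumab must be strongly considered if the participant develops a serious infection". It adds a discussion with the medical monitor and says that "guselkumab should be withheld until the clinical assessment is complete", with a pointer to Sections 5.2 and 7.1. Other rows of the table cite 7.1 in mandatory terms. For hypersensitivity: "Any participant who develops a serious hypersensitivity reaction such as anaphylaxis must discontinue guselkumab (Section 7.1". For malignancy, with a stated exception for localized basal cell cancers, participants "will be discontinued from guselkumab (Section 7.1".

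Protocol Appendix 15 item 6 deals with SARS-CoV-2 infection during the study. The investigator contacts the sponsor and considers interrupting treatment, in light of symptoms and the drugs used for COVID-19. After recovery, with all toxicities at Grade 1 or lower, resumption is discussed with the sponsor. The item does not separate serious from non-serious cases and does not mention Section 7.1.

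**The concern.** The three texts give different instructions for the same event. Guselkumab blocks IL-23, and serious infection is the first risk listed in Section 2.3.1, so this is a safety stopping rule on which sites should act alike. As written, one site could stop dosing under 7.1. Another could assess the same participant, weigh discontinuation as 2.3.1 asks, and carry on. For a participant hospitalised with COVID-19, a site could follow Appendix 15 item 6 and either not interrupt at all or restart after recovery.

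**Working it through.** No arithmetic applies, and the plan gives no figure to reproduce. The check sets the texts side by side.

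| | Section 7.1 | Section 2.3.1 risk table | Appendix 15 item 6 |
|---|---|---|---|
| Event | Serious or opportunistic infection | Serious infection | SARS-CoV-2 infection or related disease |
| Instruction | Mandatory discontinuation | Discontinuation to be strongly considered; drug withheld until assessed | Interruption to be considered |
| Restart | No provision in this entry | Left open once assessment is complete | Discussed with sponsor after recovery to Grade 1 or lower |
| Serious case singled out | Yes, it is the trigger | Yes, it is the trigger | No |

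1. *Is the 7.1 entry really mandatory?* Its stem is. Where 7.1 intends an exception it writes one: localized basal cell cancers are carved out of the malignancy entry, and a positive TB test is excused if active disease is ruled out and treatment started. The infection entry has no exception.

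2. *Is the softer verb in 2.3.1 just summary style?* No. The hypersensitivity and malignancy rows of the same table, also citing 7.1, use mandatory verbs. Withholding drug pending assessment is not itself in conflict with 7.1. The conflict is over what follows once the infection is known to be serious.

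3. *Can a COVID-19 case fall under 7.1?* Yes. Appendix 13 counts an event requiring inpatient hospitalisation as serious, and 7.1 does not exclude any organism. Item 6 covers the same participant with a weaker instruction. The overlap is limited to serious COVID-19; for a mild case the two texts do not meet.

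4. *Does any text set precedence?* The opening of Appendix 15 says that its recommendations do not override local or government requirements or the investigator's judgement; it does not mention 7.1. Appendix 12, under Protocol Amendments, allows study procedures and assessments to follow Appendix 15 under pandemic restrictions; it does not mention stopping criteria.

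5. *Does the conflict depend on whether the 7.1 stop is permanent?* Not for continued dosing: 2.3.1 and item 6 both allow a participant with a serious infection not to be stopped at all, and 7.1 does not. For resumption, the point is that item 6 describes a restart and the 7.1 infection entry does not.

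**The case against.** The best defence is that 2.3.1 is a benefit-risk summary and 7.1 the operative rule, so a site obeying 7.1 satisfies both. Appendix 15 is a temporary emergency provision, and a specific COVID-19 instruction beside a general list is ordinary drafting. There are also safeguards: sponsor contact, the Grade 1 condition before any restart, the opening of Appendix 15 requiring discontinuation if safety is considered at risk, and the 7.1 entry for investigator safety concerns. It can be added that the 7.1 infection entry is a fragment that does not fit its stem, so the documents do not prove which text is the slip. All of this limits the harm. It does not remove the mismatch, because the safeguards rest on judgement and 7.1 does not.

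Three stronger readings are tempting and are not supported.

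- *That prohibited medication shows the same contradiction.* Section 7.1 also lists "The participant receives a concomitant medication that is prohibited by the protocol", while item 6 speaks of interruption. But Appendix 15 item 1d describes discontinuation as either temporary or permanent, so an interruption can be consistent with 7.1. The SAP (5.3.2) uses flagged disallowed medications for the intercurrent events and excludes those participants from the primary analysis.
- *That the primary endpoint is materially affected.* Section 7.1 says "If a participant permanently discontinues guselkumab before Week 28, the Final Efficacy Visit should occur at the time of discontinuation". A reader could infer that the final CFR moves by 32 − 28 = 4 to 32 − 0 = 32 weeks. That is schedule arithmetic, conditional on a permanent stop and with no frequency attached. It does not measure impact.
- *That 7.1 needs a separate statement on permanence.* The contradiction over continued dosing exists either way, and aligning the texts does not require that choice.

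**Conclusion.** The contradiction is in the current text and concerns a safety stopping rule. It is confined to serious infections generally (7.1 against 2.3.1) and serious COVID-19 in particular (7.1 against Appendix 15 item 6). The conclusion assumes that 7.1, as the section devoted to discontinuation and the one cited by 2.3.1, states the intended rule.

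Its size is small. The safety summary in Protocol Section 2.2 calls serious infections infrequent, and the documents give no rate from which to project a number of affected participants. The SAP introduction records the sponsor's decision to terminate the study on 31 May 2023, and SAP Section 1.2 allows only final efficacy and final safety visits after that date. The edit is therefore now mainly a correction of the protocol text. It is worth making because it is nearly free and the rule concerns safety.

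**What to change.** Two wording changes:

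- **Section 2.3.1, serious infections row.** Replace the instruction to consider discontinuation strongly with: *is required (Section 7.1)*. Make clear that withholding applies while seriousness is being established.
- **Appendix 15 item 6.** Add: *For a serious SARS-CoV-2 infection, Section 7.1 applies.* The provisions on interruption and resumption then remain for non-serious cases.

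The cost is wording in two places, with no new data, visits or procedures, and no stop that 7.1 does not already require. The downside is that any participant with serious COVID-19 whom a site would have kept on treatment under item 6 would stop dosing.

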## 7.2. Participant Discontinuation/Withdrawal From the Study

Reasons for participant discontinuation/withdrawal from the study may include:

- Adverse event, eg, Major Adverse Cardiac Event (myocardial infarction, non-fatal stroke, or cardiovascular death)
- Lost to follow-up
- The investigator decides to withdraw the participant from the study
- Protocol violation
- Study termination by the Sponsor
- Pregnancy

- Lack of efficacy
- Withdrawal of consent
- Death

When a participant withdraws before study completion, the reason for withdrawal is to be documented in the CRF and in the source document. For each participant discontinuing the study, the investigator should attempt to obtain a CFR reading. If the reason for withdrawal from the study is withdrawal of consent, then no additional assessments are allowed.

#### Withdrawal of Consent

A participant declining to return for scheduled visits does not necessarily constitute withdrawal of consent. Alternate follow-up mechanisms that the participant agreed to when signing the consent form apply (eg, consult with family members, contacting the participant's other physicians, medical records, database searches) as local regulations permit.

Prior to a participant withdrawing consent for follow-up, the investigator should offer the participant an opportunity for one of the alternative reduced follow-up mechanisms described below. Withdrawal of consent should be an infrequent occurrence in clinical studies, therefore, prior to the start of the study the Sponsor and the investigator should discuss and reach a clear understanding of what constitutes withdrawal of consent in the context of the available reduced follow-up mechanisms listed.

